The interventions under investigation are: 1) individually tailored interdisciplinary intervention based on measures performed as part of the Cerebral Palsy follow-up Program (CPUP), other clinical examinations, standardized measurements of walking and recommendations from the gait analysis, 2) ‘care as usual’, defined by individually tailored interdisciplinary intervention based on measures performed as part of the CPUP and other clinical examinations, without recommendations from the gait analysis.

Deviations from trial protocol

Selected items of the Gross Motor Function Measure (GMFM-66) were examined at baseline and at 52-weeks follow-up to support the interpretation of the biomechanical data for the three-dimensional IGA.

GMFM-66 was not listed as an outcome measure in the study protocol (1) or in the clinical trial registration (NCT02160457). However, in the current secondary analysis, the GMFM-66 will be used as a measure of overall gross motor capacity of the child.

Study synopsis

Children with cerebral palsy (CP) often exhibit an altered gait pattern. Orthopedic surgery, spasticity management, physical therapy and orthotics are used to improve gait. Such interventions are typically planned based on clinical examinations and standardized measurements to assess walking, which in Denmark at present is the standard clinical practice ('care as usual'). However, a 3-dimensional instrumented gait analysis (IGA) will provide objective and valid measures of gait to identify features in gait and possible underlying neuro-musculoskeletal impairments (2). Using the IGA report and the interdisciplinary intervention recommendations ('the use of IGA') as part of planning an interdisciplinary intervention, the physiotherapist, orthopedic surgeons and neuro-pediatricians are provided with information on the impairments affecting gait, allowing tailored individualized treatment plans for the children and their families.

Family-centered services (FCS), where the parents are actively involved throughout setting and implementing treatment goals for individual tailored interventions for their child, is an acknowledged approach to secure the child's development and needs within the context of the child's family (3-5). The Measure of Processes of Care (MPOC-20) (3) covers families' perception of issues such as *enabling and partnership, providing general information, providing specific information about the child, respectful and supportive service and coordinated and comprehensive care* and is widely used in pediatric rehabilitation to evaluate FCS (6). However, it is uncertain if the use of IGA in the planning of individually tailored interdisciplinary intervention results in a higher perceived experience of FCS in proximity to receiving the IGA report (at 26 weeks) or a year after the gait analysis (at 52-weeks follow-up).

In children with CP, the level of gross motor function correlates with the child's extent of participation in society, school, and at home (7) as well as parent-reported quality of life (8), suggesting that impairment has a close relationship with not only social activity, but also social functionality. Although the vast majority (50-80%) of children with CP are capable of walking independently, gait performance is almost always affected as a result of musculoskeletal deformity, abnormal muscle tone, inadequate balance and impaired motor control (2). The high physical strain of walking for children with CP results in fatigue and reduced walking distance (9) as well as activity limitations (10). Overall, children with CP who display good function as determined by the GMFM-66, show a tendency toward better

functional movement, allowing them to more effectively participate in daily activities (7).

The Gross Motor Function Measure (GMFM-66), a standardized clinical tool consisting of 66 items, created to detect gross motor function change in children with CP, is considered a valid outcome measure, sensitive enough to document clinically meaningful improvement, including responsiveness (11, 12) and is the gold standard measure of functional ability in the area of CP (13). The GMFM-66 score reflects the overall level of gross motor capacity (14). Using the Gross Motor Ability Estimator Scoring Software (15), a GMFM-66 score can be obtained using a minimum of 13 items. Due to the included children's high gross motor function (GMFCS level I-II) combined with the need to limit the amount of testing time for the children, a selection of minimum 13 relevant items of the GMFM-66 were chosen for this study.

A potential association between the parents' perception of the family-centeredness of the services they and their children received during the study period (by means of the MPOC 52-weeks follow-up score) and the child's gross motor improvement (change in GMFM-66 score), could indicate that improvement in gross motor function of a child with CP is related to the parents' involvement in the process of care. Thus, an association could serve as an indicator for the health personnel in terms of detecting those families who would benefit from enhanced information, service and care, to improve the child's gross motor function.

List of abbreviations and definition of terms

BMI SDS	Body Mass Index Standard Deviation Score
CP	Cerebral Palsy
FCS	Family-centered services
GDI	Gait Deviation Index
GMFCS	Gross Motor Function Classification System
GMFM-66	Gross Motor Function Measure - 66
MPOC-20	Measure of Processes of Care – 20
IGA	Instrumented Gait Analysis
IQR	Interquartile range
SAP	Statistical Analysis Plan
SD	Standard Deviation

Study aim, hypothesis and outcome measures

Aim

The aim of this secondary analysis (on tertiary outcome measures) of a randomized controlled study is to investigate whether individually tailored interdisciplinary intervention, based on the use of IGA, has a superior effect on perceived experience of FCS compared to 'care as usual' without the use of IGA. The study will furthermore investigate whether the availability of the IGA has a superior effect on gross motor function improvement as well as investigate potential associations between perceived experience of FCS and gross motor function improvement.

Primary hypothesis and outcome

The primary hypothesis to be tested is that the use of IGA in the planning of individually tailored interdisciplinary intervention will result in a higher parentally perceived experience of FCS evaluated by the MPOC-20, compared to 'care as usual' in relatively young children with CP at GMFCS level I-II.

The primary analysis is between-group change difference in all five MPOC-20 domains at 52-weeks. The five MPOC-20 domains comprise *enabling and partnership, providing general information, providing specific information about the child, respectful and supportive service and coordinated and comprehensive care*.

Data for the primary analysis, between-group change difference in MPOC-20₀₋₅₂, will be presented in table 2.

Secondary hypotheses and outcome

a) The above listed hypothesis will be analysed at 26-weeks follow-up.

Outcome measure, between-group change difference in MPOC-20 domains at 26-weeks post start of intervention, will be presented in table 2.

b) The planning of individually tailored interdisciplinary intervention will result in better gross motor function, evaluated by GMFM-66, compared to 'care as usual' in relatively young children with CP at GMFCS level I-II.

Outcome measure, between-group change score in GMFM-66 at 52-weeks post start of intervention, will be presented in table 2.

c) The experience of FCS is associated with gross motor function improvement in a unidirectional or bidirectional relation.

Outcome will be presented as multiple regression analysis in table 3.

Statistical analyses

Data

Descriptive outcome

At inclusion the following descriptive outcomes were collected:

- Sex (female or male)
- Age (in years)
- Weight and height
(used to calculate Body Mass Index Standard Deviation Score (BMI SDS)) (16)
- Cerebral palsy spastic subtype (uni- or bilateral)
- Gross Motor Function Classification System (GMFCS level I or II)
- Randomization group: Intervention (the use of IGA) or control ('care as usual').

The descriptive outcomes will be presented in Table 1.

Outcome measures

- MPOC-20: Parent reported data obtained from a questionnaire with the five domains *enabling and partnership, providing general information, providing specific information about the child, respectful and supportive service, coordinated and comprehensive care*. Data comprise the timepoints at baseline, 26 weeks and 52 weeks post start of intervention and the differences between these timepoints: Δ MPOC-20₀₋₂₆ and Δ MPOC-20₀₋₅₂.
- GMFM-66: Standardized clinical tool created to detect gross motor function change in children with CP. Data comprise the timepoints at baseline and 52 weeks post start of intervention and the difference between these timepoints: Δ GMFM₀₋₅₂.

Data analyses

Analyses will be performed according to intention-to-treat, with last value carried forward for missing observations.

Descriptive statistics will be summarized as appropriate. Distribution of data will be investigated using normal probability plots and Shapiro–Wilk test, and will be presented with mean and standard deviation (SD) for parametric data and median and interquartile range (IQR) for non-parametric data. Data outliers will be identified with the use of scatterplots.

Between-group change differences will be estimated with a linear model (table 2, model A) in which relevant baseline scores are entered as covariates (table 2, model B). Model specifications will depend on evaluation of distributional properties of collected data and appropriate adaptation of point estimate and variation indicators.

Associations will be evaluated using multiple linear regression. To evaluate whether the child's change in gross motor function is associated to the parent's perceived experience of FCS, MPOC-20 52-weeks follow-up domain scores will be used as the dependent variable and Δ GMFM-66₀₋₅₂ score as the independent variable, adjusted for baseline GMFM-66 score (table 3, model A). Further, potential confounding variables as sex, age, BMI SDS, CP spastic subtype and GMFCS level will be adjusted for as covariates (table 3, model B).

To evaluate whether the parents perceived experience of FCS is associated with the child's change in gross motor function, Δ GMFM-66₀₋₅₂ score will be used as the dependent variable and MPOC-20 52-weeks follow-up domain scores as the independent variable, adjusted for baseline MPOC-20 domain scores (table 3, model A). Further, potential confounding variables as sex, age, BMI SDS, CP type and GMFCS level will be adjusted for as covariates (table 3, model B).

Results will be presented with an alpha of 0.05 and a 95% confidence interval, statistical significance level set at $p<0.05$.

Statistical analysis will be conducted from April 2018 and performed using Stata/IC version 14.2 or later.

Data interpretation

To investigate whether individually tailored interdisciplinary intervention based on IGA has a superior effect on perceived experience of FCS compared to ‘care as usual’, between-group change score for each of the five MPOC-20 domains will be reported in the primary analysis.

To minimize bias, interpretation of variation of outcome will be defined *a priori*:

- a) If more domains exhibit significantly positive outcomes in one group compared to the other, this group will be considered as superior.
- b) If both groups have the same number of significantly positive domains, neither group will be considered superior.
- c) If neither group has a significant positive domain, neither group will be considered superior.

Tables and figures

Table 1: Demographics and baseline data of included children

	Intervention (n=)	Control (n=)
Sex (girls/boys)		
CP spastic subtype (uni-/bilateral)		
GMFCS level (I-II)		
Age (years)		
Height (m)		
Weight (kg)		
Body Mass Index SDS		
Measure of Processes of Care – 20 domains		
enabling and partnership		
providing general information		
providing specific information about the child		
respectful and supportive service		
coordinated and comprehensive care		
Gross Motor Function Measure - 66		

Reported as mean and standard deviation (SD) or median and interquartile range (IQR).

Table 2: Between-group change difference at 26-weeks and 52-weeks follow up

	Between-group change difference											
	Model A						Model B					
	Baseline to 26 weeks			Baseline to 52 weeks			Baseline to 26 weeks			Baseline to 52 weeks		
	β (95% CI)	R ²	p	β (95% CI)	R ²	p	β (95% CI)	R ²	p	β (95% CI)	R ²	p
Δ MPOC-20 domains												
Δ enabling and partnership												
Δ providing general information												
Δ providing specific information about the child												
Δ respectful and supportive service												
Δ coordinated and comprehensive care												
Δ GMFM-66												

Dependent variable: ΔGMFM-66 or ΔMPOC-20 domains.

Independent variable: Randomization group.

Model A: Unadjusted model.

Model B: Model A adjusted for relevant baseline score.

Abbreviations: GMFM – Gross Motor Function Measure. MPOC – Measure of Processes of Care.

Table 3: Associations between MPOC-20 and GMFM-66

Dependent variable:	Independent variable: ΔGMFM_{0-52} score	Model A			Model B		
		β (95% CI)	R ²	p	β (95% CI)	R ²	p
MPOC-20 52-weeks follow-up domain scores							
enabling and partnership							
providing general information							
providing specific information about the child							
respectful and supportive service							
coordinated and comprehensive care							

Dependent variable: MPOC domains at 52-weeks follow-up.

Independent variable: ΔGMFM_{0-52} score.

Model A: Adjusted for baseline GMFM.

Model B: Model A adjusted for sex, age, BMI SDS, CP type and GMFCS level.

Abbreviations: GMFM – Gross Motor Function Measure. MPOC – Measure of Processes of Care.

Dependent variable:	Independent variable: MPOC-20 52-weeks follow-up domain scores	Model A			Model B		
		β (95% CI)	R ²	p	β (95% CI)	R ²	p
ΔGMFM_{0-52} score							
enabling and partnership							
providing general information							
providing specific information about the child							
respectful and supportive service							
coordinated and comprehensive care							

Dependent variable: ΔGMFM_{0-52} score

Independent variable: MPOC domains at 52-weeks follow-up

Model A: Adjusted for baseline MPOC-20 domain scores

Model B: Model A adjusted for sex, age, BMI SDS, CP type and GMFCS level.

Abbreviations: GMFM – Gross Motor Function Measure. MPOC – Measure of Processes of Care.

Literature

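### Secondary hypothesis c) is one claim assessed by 20 correlated p-values at 0.05 with no rule for deciding it, so its false-positive risk is well above the stated 5%

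*SAP*

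**What the plan says.** Under Secondary hypotheses and outcome, item c) reads "The experience of FCS is associated with gross motor function improvement in a unidirectional or bidirectional relation". Its outcome is given only as "Outcome will be presented as multiple regression analysis in table 3".

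Data analyses describes two regressions. In the first, "MPOC-20 52-weeks follow-up domain scores will be used as the dependent variable", with GMFM-66 change as the independent variable and baseline GMFM-66 as a covariate. In the second the roles are reversed and the covariate is baseline MPOC-20. Each has a Model A and a further-adjusted Model B; the Table 3 footnote reads "Model B: Model A adjusted for sex, age, BMI SDS, CP type and GMFCS level". Table 3 prints a coefficient with its interval, an R² and a p-value for every domain under each model.

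One sentence sets the level for everything: "Results will be presented with an alpha of 0.05 and a 95% confidence interval". Data interpretation fixes rules in advance, but for the randomised comparison, where "between-group change score for each of the five MPOC-20 domains will be reported in the primary analysis". Those rules count the domains that favour one group over the other.

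**The concern.** Hypothesis c) has one answer, but its table gives 20 chances at p<0.05 and the plan does not say how they combine. The pre-set rules cannot be borrowed, because c) contains no contrast between groups. The disjunction in c), one direction or both, leaves it open whether a result in either half of Table 3 would be enough.

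The reverse regression is also not independent evidence about direction. With identical covariates, regressing Y on X and X on Y gives the same p-value for the slope. The two halves of Table 3 differ only because one adjusts for baseline GMFM-66 and the other for baseline MPOC-20.

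The stake is practical. The Study synopsis says that an association could help staff to detect families who would benefit from more information, service and care. If c) were declared supported by a chance result, that suggestion would rest on it.

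**Working it through.** **Inputs from the SAP.** Five MPOC-20 domains; two directions; two models; 0.05 per test (taken as two-sided from the 95% interval); no adjustment. The SAP states no error rate for c) as a whole, so there is no figure to reproduce.

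**Count.** 5 × 2 × 2 = 20 p-values. This takes one regression per domain in the second direction. The text there could be read as one model with all domains, but Table 3 gives a separate R² and p for each row.

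**Benchmark if the tests were independent.** 1 − 0.95^k:
- k = 5: 22.6%
- k = 10: 40.1%
- k = 20: 64.2%

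**Allowing for dependence.** The tests share data, so the k = 20 benchmark is too high. The Table 3 regressions were simulated with no link between MPOC-20 and GMFM-66, 3,000 runs per setting. Assumptions, none given in the SAP: n as shown; equal correlation between domains; MPOC-20 baseline-to-52-week correlation 0.5; correlation of −0.3 between baseline GMFM-66 and its change; five null covariates in Model B. Chance of at least one p<0.05:

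| n | Domain correlation | 5 tests (Model B, first direction) | 10 tests (Model B, both directions) | All 20 |
|---|---|---|---|---|
| 40 | 0 | 22.0% | 31.3% | 39.9% |
| 40 | 0.5 | 16.7% | 25.3% | 33.5% |
| 40 | 0.9 | 9.7% | 15.0% | 19.4% |
| 60 | 0 | 23.4% | 33.5% | 39.9% |
| 60 | 0.5 | 19.2% | 27.5% | 33.3% |
| 60 | 0.9 | 10.3% | 15.2% | 19.1% |

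A second set of runs, with GMFM-66 baseline-to-52-week correlation 0.8, gave 11-24% for five tests and 20-41% for all 20 at n = 60. At n = 40 it gave 20-43% for all 20. Together the results are about 10-24% and about 19-41%, with the top end slightly higher at n = 40. At n = 80 they hardly change (18.6-39.4% for all 20). At n = 60 and domain correlation 0.7, varying the other correlations gives 24-29%.

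The expected number of false positives is 20 × 0.05 = 1. The chance of at least one is far below 64% because they cluster.

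**Effect of a rule.** One direction and Model B, with its five domains at 0.05/5 = 0.01 (Holm's first step): 2.1-5.2%. Naming the direction and model but leaving the five domains at 0.05: still about 10-23%.

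**Power cost of Holm.** Assume a partial correlation of 0.35 in the second direction, Model B. Its seven regressors leave six conditioning variables, so z = atanh(0.35) × √(n − 6 − 3).
- n = 60: z = 0.3654 × √51 = 2.61. Power is Φ(2.61 − 1.96) = 74% at 0.05 and Φ(2.61 − 2.576) = 51% at 0.01.
- n = 40: z = 0.3654 × √31 = 2.03. Power is 53% and 29%.

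**The case against.** Four points on the other side deserve weight.

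**The 20 p-values are not 20 questions.** Model B extends Model A by adding confounders, and the two directions probe nearly the same partial association. This stands. At n = 60 and domain correlation 0.5, five tests already give about 19% and the other 15 raise it only to about 33%. Most of the excess is ordinary five-domain multiplicity.

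**The SAP does not say that one significant domain supports c).** This also stands. A reader might infer it from the wording of c), but it is an inference from a gap. Read domain by domain, each test keeps its 5%, and all results are to be shown, so none can be picked silently. But c) is worded as one claim about the experience of FCS, and a domain-by-domain reading does not say when that claim is met.

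**The exploratory character is largely conveyed.** The study is called a secondary analysis on tertiary outcomes, GMFM-66 is disclosed as absent from the protocol and registration, and the synopsis speaks of potential associations. This softens the tone and lowers the severity. It does not fix the inferential status: c) is a listed hypothesis with a significance level, and the SAP never calls it exploratory.

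**Correction costs power.** It does, as shown, so Holm should not be the only remedy offered.

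**Conclusion.** The point holds in a limited form. The plan names no deciding result, testing order, correction or exploratory label for c). When no association exists, the chance of at least one p<0.05 is two to almost five times the stated 5% on the narrowest reading (about 10-24%) and about four to eight times over the whole table (about 19-41%). The sample size and all correlations behind these ranges are assumptions; the result depends mainly on how strongly the domains correlate and little on n.

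A reader might infer that a false association is likely, or quote 64%. The documents do not support that. The 64% needs 20 independent tests, which Table 3 rules out by construction, and every simulated setting is below 50%. The rates also apply only if there is truly no association.

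Severity is minor to moderate: c) is the last of three secondary hypotheses and full reporting is planned. Because these are different models answering a different question, changing the rule for the five primary domains would not settle it.

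**What to change.** Amend Data analyses and Data interpretation in one of two ways.

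1. **Give c) a deciding result.** Name one regression, for example Model B in one stated direction. Claim an association only if a joint test of the five domains is significant at 0.05, or by domain after Holm over the five. Report the other model and the reverse regression as supportive estimates with 95% confidence intervals. Naming the regression without one of these rules is not enough.
2. **Label c) exploratory and hypothesis-generating**, and make no significance claim for it.

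Either takes a few sentences, and Holm adds one column to Table 3; no new data are needed. Under Holm, per-domain power falls noticeably (74% to 51% in the example above), and a single domain with p between 0.01 and 0.05 may no longer support c). The joint test avoids the per-domain threshold but does not say which domain is responsible.

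The joint test is also easier in one direction. With MPOC-20 as the outcome, Model B has eight coefficients per equation (intercept, GMFM-66 change, baseline GMFM-66, five covariates). With GMFM-66 change as the outcome, five domains, their five baselines, five covariates and the intercept make 16, which is many for an n of 40 to 60. The exploratory label has no power cost but gives up a confirmatory statement on c).

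### The model and point estimate for the primary MPOC-20 comparison are left open until the outcome data are in, so 5% control per domain is not assured

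*SAP*

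**What the plan says.** Under Primary hypothesis and outcome: "The primary analysis is between-group change difference in all five MPOC-20 domains at 52-weeks". Under Data analyses the default method is given: "Between-group change differences will be estimated with a linear model (table 2, model A) in which relevant baseline scores are entered as covariates" (the latter being Model B). The notes to Table 2 confirm that Model A is unadjusted and Model B adds the relevant baseline score.

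The next sentence reopens that choice: "Model specifications will depend on evaluation of distributional properties of collected data and appropriate adaptation of point estimate and variation indicators".

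Two data checks come earlier in the section. "Distribution of data will be investigated using normal probability plots" and the Shapiro-Wilk test, and that sentence ties the checks to presenting mean and SD or median and IQR. Also, "Data outliers will be identified with the use of scatterplots".

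The testing level is stated thus: "Results will be presented with an alpha of 0.05 and a 95% confidence interval, statistical significance level set at" p<0.05. Data interpretation then gives the decision rule, introduced with "To minimize bias, interpretation of variation of outcome will be defined" in advance. Its first limb reads: "If more domains exhibit significantly positive outcomes in one group compared to the other, this group will be considered as superior".

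**The concern.** This is not a detail left to the protocol. The SAP itself states a rule for the primary comparison, and the rule depends on the data. The Introduction says that the 52-week examinations were complete in July 2017, and Data analyses starts the analysis in April 2018, so the choice is made with every outcome in hand.

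The clause covers the point estimate as well as its precision. Adapting the point estimate can change what is being estimated, for example from a mean difference to a median or rank contrast.

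Under rules a) to c), a single domain crossing p<0.05, with none the other way, settles the primary verdict. The SAP fixes in advance how p-values are counted, but not how they are produced. An open choice of specification, or an open choice between Models A and B, could create or remove that one crossing. That works against the stated purpose of limiting bias.

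**Working it through.** **The plan's own figure.** The only relevant figure is the 0.05 level, which is an input. The SAP gives no sample size, effect size or power, so there is nothing to reproduce.

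**What is fixed and what is open**

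| Item | In the SAP |
|---|---|
| Outcomes | Fixed: five domain changes at 52 weeks |
| Level | Fixed: 0.05 per test, no adjustment stated |
| Default model | Linear, A and B both reported; which one counts is not stated |
| Criterion for leaving the default | None |
| Fallback model or estimate | None named |
| Masking to group when choosing | Not stated |
| Same method for all domains | Not stated |

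**Simulation under no group difference.** The following are assumptions:
- 15, 20, 30 or 40 children per arm.
- Scores bounded at 1-7 or log-normal, plus normal scores at 20 per arm.
- Between-domain correlation 0.6, plus 0 at 20 per arm.
- Baseline-to-follow-up correlation 0.5.

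This makes 12 settings of 2,000 trials each. Each domain was tested with Model A, Model B and a rank test on change. False superiority means unequal counts of significant domains for the two groups.

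| How the counted p-value is obtained | Error per domain | False superiority |
|---|---|---|
| One method fixed in advance | 3.5-5.2% | 13-23% |
| Mechanical rule: Shapiro-Wilk on residuals, then linear or rank | 4.4-5.7% | 16-23% |
| Smaller p of Model A and rank test | 5.6-7.0% | 19-26% |
| Smaller p of Models A and B | 5.6-7.7% | 21-30% |
| Smallest p of Model A, Model B and rank test | 7.3-8.9% | 26-33% |

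The values below 4.7% for a fixed method come from the log-normal settings; for normal or bounded scores the fixed range is 4.7-5.2%. For the choice between A and B, normal or bounded scores give 7.1-7.7% and log-normal scores 5.6-6.6%.

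Monte Carlo error: 2,000 × 5 = 10,000 tests per setting. The standard error of a 5% rate lies between √(0.05 × 0.95 / 10,000) = 0.22 and √(0.05 × 0.95 / 2,000) = 0.49 percentage points, depending on how correlated the domains are.

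**Second simulation**, at an assumed 20-30 per arm with the same correlations: 4.3-5.4% for fixed Model B, 4.3-5.7% for a mechanical Shapiro-Wilk switch and 6.9-8.2% for a results-guided choice. False superiority rose from 15-19% to 23-28%.

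**Separating the two sources of error.** With five independent domains at 0.05, the chance of at least one false positive is 1 − 0.95⁵ = 1 − 0.774 = 22.6%, with no freedom of choice at all. In one setting (20 per arm, bounded scores, correlation 0.6), Model B fixed gives 18.0% false superiority and the smallest of three p-values gives 26.7%. The choice adds 26.7 − 18.0 = 8.7 points; the other 18.0 come from the counting rule.

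**The case against.** The strongest reply is that the clause ties the choice to distributional properties, not to results. If it were applied mechanically with the Shapiro-Wilk test already named, the error would stay near 5%. That stands. A reader might infer that the p-values fail the 5% level, but the SAP does not prescribe a results-guided choice. It only leaves room for one, because the named checks are linked to presentation of the data and no threshold links them to the model.

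Other stronger readings are also unsupported:

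- **A different model for each domain.** The text does not say this, and the Table 2 shell gives every row the same columns. A common method is simply not required.
- **Outliers removed.** The SAP says that they are identified, and the section opens with intention-to-treat. No removal step is stated, so error rates for dropping points do not describe this plan.
- **Power lost through a rank test.** No rank test of the group difference is named, and several possible adaptations would keep the baseline covariate.
- **False superiority of 13-23% caused by this clause.** That baseline arises from five unadjusted domains.

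It is also fair to say that this is a secondary analysis on tertiary outcomes, which limits the consequence. Finally, the sentence introducing the linear model might be read as leaning towards Model B. But Table 2 reports both models and nothing says which one enters the count.

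**Conclusion.** The point holds in limited form. The primary model and estimate are not fixed before the outcome data are complete, and the SAP does not choose between Models A and B, so control at 5% per domain is not assured. If the choice follows the results, the error is about 7-8% per domain. It can be as low as 5.6% (two options, log-normal scores) and as high as 8.9% (three options). If the choice is fixed or purely mechanical, the error stays near 5%. Choosing between A and B alone accounts for much of the possible inflation.

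The wording of the SAP establishes the defect. Its size rests on assumed arm sizes, distributions and correlations, none of which the SAP supplies. The error from counting five domains without adjustment is larger, is separate, and remains after this fix.

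**What to change.** Replace the sentence on model specifications with:

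> The between-group mean difference in all five MPOC-20 domains and in GMFM-66 is estimated with the baseline-adjusted linear model (Table 2, Model B), whatever the distribution of the data, and only Model B p-values at 52 weeks for the MPOC-20 domains are counted in rules a) to c). If residual diagnostics, done with group masked, show marked departures, the same mean difference is reported with robust (for example HC3) standard errors for all domains. Model A and any rank-based or quantile analysis are sensitivity analyses and are not counted. Values flagged on scatterplots are checked against source and kept.

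Model B is the better choice on precision. With equal variances at both times and baseline-to-follow-up correlation r, its variance relative to Model A is (1 − r²) / (2(1 − r)) = (1 + r)/2. That is 0.75 at an assumed r = 0.5, and 0.65-0.85 for r = 0.3-0.7.

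The cost is SAP wording and, if robust errors are used, one Stata option. Robust errors are optional. Their downside is slight conservatism: HC3 gave 3.9-4.6% instead of 5% at about 20 children per arm in simulation. Judging what counts as a marked departure still needs discretion, but masking, one estimate and one method for all domains leave little room for the result to steer it.
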